1.2 Trial design

A two stage, open label, randomized (1:1:1) controlled trial with formal interim analysis after 171 participants (57 per arm) which also includes an informal interim analysis after 30 participants (10 per arm) complete follow-up. Due to the three different stages in this trial, the MATIS SAP is separated into two sections. The aim of this statistical analysis plan (SAP) is to describe in detail the analysis that will be undertaken for the formal interim analysis and final analysis. The informal interim analysis was to provide an early opportunity to check the dosing regimen, see MATIS SAP I – Dose Verification for a detailed description of the statistical analysis conducted at this stage.

[figure not shown]

Figure 1: Schematic of study Design

Treatment is for 14 days from baseline. Patients will receive follow-up assessments at 1, 7, 14 and 28 days after the first dose. The time allowed for screening assessments allows time for eligibility assessments to be included.

- Screening Period: up to 7 days to the day of randomisation
- Treatment Period: 14 days
- Follow-up period: Day 14 to 28

Patients who have recovered and are fit for discharge from hospital during the treatment period, will be discharged home with trial medication to complete a fixed 14 day course. Such patients will be followed up weekly with telephone monitoring until day 28 and additional blood test monitoring where practically possible.

Table 1. Study visits

Table 1. Study visits	Screening	Baseline				Last
Study Day	-6 to 0	0	1+	7 #	14#	visit 28 #
Time window		-2 days	+1	± 3	± 3	± 3
		,	day	day	day	day
Informed consent	X					-
Inclusion/Exclusion criteria	X	X				
Demographic data	X					
Medical history including major	X					
comorbidities						
Physical exam	X					
COVID-19 diagnosis, duration and	X					
severity						
Pregnancy test	X					
Vital signs	X	X	X	X	X	X
NEWS score	X	X	X	X	X	X
Inflammatory markers (CRP, D-dimer,		X	X	X	X	X
LDH, ferritin, full blood count)						
PK levels*					X	X
Full blood count¶		Daily while on CYP3A4 inhibitor				
FiO ₂	X	X	X	X	X	X
SpO ₂ and/or PaO ₂	X	X	X	X	X	X
Randomisation		X				
Weight and Estimated height		X				
Safety monitoring of liver and renal	X	X	X	X	X	X
function						
Length of stay						
Serious Adverse Events	X	X	X	X	X	X
Concomitant medications	X	X	X	X	X	X
Serum		X		X		X
Plasma		X		X		X
RNA in PAX gene tube		X		X		X
PBMC		X		X		X
Nasosorption biomarkers		X		X		X

⁺ data that is routinely collected for clinical purposes will be recorded and a visit is not required

[#] in the event that the patient recovers from COVID19 and is discharged, these visits will not be mandated. Instead a visit should occur on the date of discharge. Where possible, patients will be contacted by telephone at day 7, 14 and 28 and invited to attend for blood tests to monitor resolution of illness.

^{*}Ruxolitinib dose for these patients will be assessed after 10 dialysis patients complete Day 14 through pharmacokinetics (PK) levels which will be assessed.

For patients randomized to ruxolitinib and prescribed a strong CYP3A4 inhibitor or dual CYP3A4/CYP2C9 inhibitor. Please refer to Section 7.8 of study protocol v1.9 for details.

1.3 Study population

1.3.1 Eligibility criteria

Inclusion criteria

- Patients age ≥ 18 years at screening.
- Patients meeting criteria of:
 - o Hospitalization AND
 - o SARS-CoV2 infection (clinically suspected¹ or laboratory confirmed) AND
 - o Radiological change consistent with COVID-19 disease
- Mild or moderate (Grade 3 or 4 severity by modified WHO COVID-19 Ordinal Scale) C19 pneumonia.
- $CRP \ge 30 \text{mg/L}$ at any time point.
- Informed consent from patient or personal or professional representative.
- No medical history that might, in the opinion of the responsible clinician, put the patient at significant risk if he/she were to participate in the trial.
- Agreement to abstain from sexual intercourse or use contraception that is >99% effective for all participants of childbearing potential for 42 days.²
- For male participants, agreement to abstain from sperm donation for 42 days after the last dose of study drug.³
- Non-English speakers will be able to join the study. If patients are unable to understand verbal
 or written information in English hospital translation services will be requested at the
 participating site for the participant where possible.
- Patients normally on non-invasive ventilation such as continuous positive airway pressure (CPAP) at home are eligible.

¹ Clinical suspicion of COVID-19 pneumonia will be confirmed by two independent clinicians.

² Females must be either post-menopausal for at least 1 year or surgically sterile; or if female of child-bearing potential, must not be pregnant or lactating and must agree to use an acceptable method of birth control throughout the duration of the trial and for 30 days following the last dose. Acceptable methods of birth control are defined as: hormonal contraception (pill, injection or implant) used consistently for at least 30 days prior to enrollment, intrauterine device (IUD), double-barrier (ie, condom and spermicide, or condom and diaphragm), or true abstinence (when this is in line with the preferred and usual lifestyle of the subject).

³ Male subject with a partner of childbearing potential must agree to use an appropriate double-barrier method of contraception during the time interval between administration of the first dose of study drug and 30 days following the last dose, or must agree to true abstinence (when this is in line with the preferred and usual lifestyle of the subject).

Exclusion criteria

- Requiring either invasive or non-invasive ventilation including CPAP or high flow nasal oxygen at any point after hospital admission and before baseline not related to a pre-existing condition (e.g. obstructive sleep apnoea)
- Grade \geq 5 severity on the WHO COVID-19 Ordinal Scale.
- O_2 saturation < 90% on \ge 60% inspired oxygen at baseline.
- In the opinion of the investigator, progression to death is inevitable within the next 24 hours, irrespective of the provision of therapy.
- Any medical condition or concomitant medication that in the opinion of the investigator would compromise subjects' safety or compliance with study procedures.
- Any medical condition which in the opinion of the principal investigator would compromise the scientific integrity of the study.
- Known severe allergic reactions to the investigational agents.
- Use of drugs within the preceding 14 days that are known to interact with any study treatment (FOS or RUX), as listed in the Summary of Product Characteristics.
- Child Pugh B or C grade hepatic dysfunction.
- Pregnant or breast feeding.

1.4 Treatment groups

1.4.1 Standard of care

It is accepted that SOC may change during a rapidly evolving pandemic. Co-enrolment to other trials and rescue therapy, either pre- or post-randomisation, is permitted.

1.4.2 Future changes to Standard of Care

The study team will remain cognisant of the prevailing global literature during the current pandemic on effective therapies for COVID-19 pneumonia. If a treatment emerges with efficacy and safety profile that is superior to SOC then options for adoption of the new therapy as SOC will be discussed with the DMC. Specifically, the impact that the new SOC might have on original trial statistical parameters and outcomes measures will be considered noting that SOC is received by participants in all three arms.

1.4.3 Ruxolitinib

Table 2. Ruxolitinib (RUX)

Period	Dose	Frequency
Day 1-7	10mg	Twice daily
Day 8-14	5mg	Twice daily

1.4.4 Fostamatinib

Table 3. Fostamatinib (FOS)

Period	Dose	Frequency
Day 1-7	150mg	Twice daily
Day 8-14	100mg	Twice daily

1.4.5 Treatment duration

The planned duration of treatment is 14 days. Participants may be discontinued from treatment earlier due to unacceptable toxicity or disease progression, which will be recorded as serious adverse events (SAEs). If a participant is discharged prior to day 14 they will go home and continue with the treatment plan.

1.5 Sample size estimation

In the following Stage 1 refers to the formal interim analysis after 171 participants have been recruited and completed 14 days of follow-up. Stage 2 refers to the final analysis when recruitment and follow-up are complete, and it includes all the participants.

171 (57 per arm) patients with COVID-19 pneumonia will be recruited to Stage 1, if the trial progresses to Stage 2 an additional maximum of 285 (95 per arm) will be recruited, resulting in a potential sample size of 456 if three trial arms continue for the whole trial (152 per arm). These numbers have been chosen to provide power of 90% (minimum marginal power) with a maximum 5% chance of an intervention arm being recommended when it provides no improvement over control (5% one-sided family-wise error rate) and has been inflated by 5% for missing outcome data. Patients will be enrolled into RUX, FOS or SOC groups, as shown in figure 1.

The trial is designed to compare two experimental treatment arms to a shared control arm, with equal treatment allocation over two unequally spaced stages. Stage one will be undertaken after 37.5% of maximum sample size have been recruited and completed follow-up. A separate stopping rule will be

used which means the trial will continue until a decision is made for all experimental treatment arms. The sample size in each stage is allowed to vary according to the number of treatments present. The sample size calculation is based on the calculation in the R Shiny app for multi-stage group-sequential multi-arm clinical trials for a Bernoulli distributed primary outcome found here https://mjgrayling.shinyapps.io/multiarm/ but with an inflation to allow for unequal allocation across stages (0.375 of maximum possible sample in stage 1 and 0.625 of sample in stage 2).

1.5.1 Sample size for formal interim analysis (Stage 1)

Current rate of severe pneumonia in the standard of care is 50%. In the case that an experimental arm reduces this to 30% (relative risk, RR, 0.6), then the design provides a 92% chance (one-sided alpha of 0.25, equivalent to stopping for futility if the one-sided p-value is >0.25) of it being recommended to continue to stage 2.

The design recommends stopping an intervention arm at stage 1 if the one-sided p-value is >0.25 but this is a non-binding rule (i.e. the overall power is calculated assuming this rule is always followed and the family-wise error rate (FWER) is calculated assuming it is not followed). The actual FWER will be lower if the rule is always followed).

Recruitment to the trial will continue during this interim analysis stage.

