#### Interim analysis (Stage 1)

The aim of the Stage 1 interim analysis is to provide an opportunity to stop enrolling patients to an intervention arm that is not showing sufficient promise of efficacy. The Stage 1 review will be undertaken by a statistician that is independent of ICTU and overseen by the data monitoring committee who will advise on whether the trial should continue with both intervention arms, with one intervention arm, or stop at this stage. This decision will be based on a suggested one-sided p<0.25 although interpretation of the p-value will be on the continuous scale as strength against the null hypotheses and will not be restricted to a single binary threshold. Our sample size calculations for both stages ensure we have a good prospect of these achieving these aims.

Current rate of severe pneumonia in the standard of care is 50%. In the case that an experimental arm reduces this to 30% (relative risk, RR, 0.6), then the design provides a 92% chance (one sided alpha 0.25) of it being recommended to continue to stage 2.

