3.1 Primary outcome of the main study - Modified WHO grading

3.1.1 Definition of the primary outcome

The proportion of participants progressing from mild to severe COVID-19 pneumonia within 14 days. Where severe COVID-19 pneumonia is defined by a modified WHO COVID-19 Ordinal Score ≥ 5 (on the 9 point scale), comprising the following indicators of disease severity: Death (9) OR Requirement for invasive ventilation plus organ support (8) Requirement for invasive ventilation (7) OR Requirement for non-invasive ventilation including CPAP or high flow oxygen (6) OR O₂ saturation < 90% on \geq 60% inspired oxygen (5). These are captured in the database as follows:

Modified WHO COVID-19 Ordinal Score	Database
(9) Death	
(8) Requirement for invasive ventilation plus organ support	Has the patient required renal replacement therapy? OR Has the patient required ECMO? OR Has the patient required inotropic support? AND Has the patient required intubation and mechanical ventilation?
(7) Requirement for invasive ventilation	Has the patient required intubation and mechanical ventilation?
(6) Requirement for non-invasive ventilation including CPAP or high flow oxygen	Has the patient required NIV, CPAP or high flow nasal oxygen?
(5) O ₂ saturation < 90% on ≥60% inspired oxygen	Has the patient's oxygen saturation been < 90% on 60% inspired oxygen?

3.1.2 Statistical model at stage 1

The stage one primary analysis will consist of fitting two separate binomial regression models for the RUX vs SOC and FOS vs SOC comparisons in order that we can undertake an adjusted analysis using a propensity score approach. Specifically a generalized linear model with WHO COVID-19 status (<5 or ≥ 5) as the outcome and treatment group as a covariate. We will adjust the treatment effect for the

following prespecified covariates using a propensity score approach. The propensity score model will include:

- baseline WHO COVID-19 score (3 or 4)
- age ($<65 \text{ or } \ge 65$)
- receipt of dexamethasone (prior randomisation or up to 1 day post randomisation)
- receipt of tociluzimab (prior randomisation or up to 1 day post randomisation)

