The stage two primary analysis will consist of fitting one binomial regression model regardless of whether one or two experimental treatments progress from stage one. Specifically a generalized linear model with WHO COVID-19 status (<5 or \ge 5) as the outcome and treatment group, baseline WHO COVID-19 score (3 or 4), age (<65 or \ge 65), receipt of known effective treatments dexamethasone and/or tociluzimab, prior vaccination against COVID-19 (y/n) and receipt of paxlovid and/or molnupiravir at the time of or prior to randomisation into MATIS as covariates will be fitted. Effective treatments will be included as separate covariates in the primary analysis model. Given the anticipated small number of sites in this study, site will also be included in the model as a fixed effect. In the event that all participants are on one of the effective treatments that covariate will be removed from the model.

If including site as a fixed effect results in unstable model estimates e.g. if there are a number of sites with very few randomisations we will exclude site from the model and we will only adjust for baseline WHO COVID score, age group, receipt of known effective treatments dexamethasone and/or tociluzimab, prior vaccination against COVID-19, and receipt of paxlovid and/or molnupiravir.⁶ We will also consider not adjusting for paxlovid and/or molnupiravir if the number of participants receiving these are low. If after removing sites and treatments the model is not stable due to event rate:covariate ratio we will adjust for all covariates using a propensity score approach.

The model will be fitted with a binomial distribution and logit link function and the treatment effect will be reported as an odds ratio with corresponding 95% confidence interval and p-values. P-values will be one-sided and judged at the 0.027 level. Therefore, a two-sided p-value < 0.054 will be used to indicate a significant treatment effect.

The stage two model to be fitted to estimate the treatment effects will be:

$$logit(\pi_{ij}) = \beta_{0} + \beta_{1}RUX_{ij} + \beta_{2}FOS_{ij} + \beta_{3}WHO_{ij}^{0} + \beta_{4}AGE_{ij}^{0} + \beta_{5}DEX_{ij}^{0} + \beta_{6}TOC_{ij}^{0} + \beta_{7}VAC_{ij}^{0} + \beta_{8}PAX_{ij}^{0} + \beta_{9}MOL_{ij}^{0} + \beta_{10}SITE_{1} + \beta_{11}SITE_{2} + \cdots + \beta_{12}SITE_{i-1}$$

 RUX_{ij} : dummy variable for treatment ($RUX_{ij} = 0$ or 1) for participant i in jth site

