We will undertake an exploratory analysis to examine the treatment effect (reported as a risk ratio (RR)) adjusted for compliance. This will be achieved through a complier adjusted case (CACE) analysis using a two-stage residual inclusion estimator (2SRI) approach with randomisation group as the instrumental variable. The primary analysis model described in 3.1.3 will be refitted with the log link function (instead of logit function) to give the treatment effect as a RR with corresponding 95% confidence interval and p-values. The CACE will then be estimated for this model and we will compare the CACE estimates of the RR to the RR obtained from the refitted primary analysis model. Randomisation meets the criteria for an adequate instrument variable since (i) randomisation predicts the treatment receipt, (ii) randomisation is unconfounded with the outcome and we assume (iii) no direct effect of randomisation on the outcome (other than via treatment receipt) – *the exclusion restriction*. After the second stage of estimation, the standard errors of the estimates will be corrected using the method of Terza. ^{9, 10}

This approach can only include adherence information in the intervention groups as the equivalent usage in the control participants is not recorded (as the control intervention is SOC and can differ between participants and is likely to evolve with time). SOC will be assumed to be 100% compliant with prescribed treatment.

We will define a complier as an individual who receives $\geq 90\%$ of prescribed dose. In addition to the analysis using a 90% threshold to define compliance we will undertake alternative analysis defining a 'complier' as an individual who receives $\geq 60\%$, $\geq 70\%$ and $\geq 80\%$ of prescribed dose to explore the impact of alternative definitions of compliance.

Analysis will adjust for baseline WHO COVID-19 score (3 or 4), age (<65 or ≥65)), receipt of known effective treatments dexamethasone and/or tociluzimab, prior vaccination against COVID-19, and receipt of paxlovid and/or molnupiravir at the time of or prior to randomisation into MATIS and site as fixed as per the primary analysis model described in section 3.1.3. The model will be modified in a similar manner as the primary outcome modelling in the event of low event rates.

iv. Time of enrolment

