An exploratory analysis of the primary outcome will be undertaken in order to assess the impact of time of enrolment. A categorical variable will be created by splitting the recruitment period into quartiles such that participants are grouped into approximately four equal sized groups based on time of enrolment into the MATIS study. This variable will then be included as a covariate in the primary analysis model described above as a treatment group-by-time interaction term to assess the impact of time of recruitment on the treatment effect estimate.

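### Does sizing the trial on a single 50% control rate leave it underpowered if standard of care improves?

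*SAP*

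**What the plan says.** SAP 1.5.1 states "Current rate of severe pneumonia in the standard of care is 50" per cent and takes 30% (relative risk 0.6) as the target for an effective arm. With 57 per arm at stage 1 and a one-sided guide of 0.25, it gives a 92% chance of continuing. SAP 1.5.2 gives 90% overall power with 152 per arm and a one-sided final threshold of 0.027. Power there means passing stage 1 and also succeeding at the end. The protocol's paragraph on the Stage 1 interim analysis (section 4.1) adds: "Our sample size calculations for both stages ensure we have a good prospect of these achieving these aims".

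On changing care, SAP 1.4.2 and Protocol 7.2 say that if a superior therapy emerges its adoption will be discussed with the DMC, and "the impact that the new SOC might have on original trial statistical parameters and outcomes measures will be considered".

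The models allow for other treatments. The stage 1 propensity score (SAP 3.1.2) includes dexamethasone and "receipt of tociluzimab (prior randomisation or up to 1 day post randomisation"). The stage 2 model (SAP 3.1.3) includes "receipt of known effective treatments dexamethasone and/or tociluzimab, prior vaccination against COVID-19 (y/n) and receipt of paxlovid and/or molnupiravir", with the provision "In the event that all participants are on one of the effective treatments that covariate will be removed from the model". SAP 3.1.5 adds, for its mediation and compliance models, "The model will be modified in a similar manner as the primary outcome modelling in the event of low event rates", and also plans: "An exploratory analysis of the primary outcome will be undertaken in order to assess the impact of time of enrolment".

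**The concern.** The analysis sections seem to accept that background care has moved on, while the sample size section still calls 50% current. The sizes of 171 and 456 and the 90% also appear unchanged in the protocol's amendment dated 14 August 2020. The promise to consider the effect of new care carries no number, date or decision rule, and both looks are set by headcount.

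If effective treatments lowered the event rate in every arm, a fixed number of patients would yield fewer events. Power would then fall for a constant relative risk or odds ratio, the two scales the documents use. Timing matters too. Because power requires passing stage 1, the chance of passing stage 1 caps overall power. Once stage 1 is judged at 57 per arm, a larger stage 2 might not restore 90%. At stake would be the dropping of an effective arm, or a null result read against a 90% that no longer applied.

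**Working it through.** **Inputs.** SAP 1.5 to 1.5.2: 57 and 152 randomised per arm, 5% missing outcomes, one-sided 0.25 (z = 0.674) and 0.027 (z = 1.927), 50% versus 30%. Evaluable per arm: 0.95 × 57 ≈ 54 and 0.95 × 152 ≈ 144. Control rates of 40% and 30% are assumptions; the documents give no observed rate.

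**Formula.** At each look, pass probability = Φ(d / SE − z), with d = p₁ − p₂ and SE = √{[p₁(1−p₁) + p₂(1−p₂)] / n}. Overall power is the joint probability of passing both looks under a bivariate normal with correlation √0.375 = 0.612.

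**The plan's own figures, 50% versus 30%.**
- Stage 1: SE = √(0.46/54) = 0.0923; 0.20/0.0923 − 0.674 = 1.49; Φ = 93.2% (stated 92%).
- Final look alone: SE = √(0.46/144) = 0.0565; 0.20/0.0565 − 1.927 = 1.61; Φ = 94.6%.
- Both: 89.9% (stated 90%). With everyone evaluable (57/152) it is 91.2%.

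**Lower control rates.** The design odds ratio is (0.3/0.7)/(0.5/0.5) = 0.4286. At a 40% control rate with relative risk 0.6 held, for example, stage 1 SE = √(0.4224/54) = 0.0884; 0.16/0.0884 − 0.674 = 1.13; Φ = 87.2%.

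| Control / treated | Held constant | Stage 1 pass (ceiling) | Final alone | Both |
|---|---|---|---|---|
| 50 / 30 | design | 93.2% | 94.6% | 89.9% |
| 40 / 24 | relative risk 0.6 | 87.2% | 84.8% | 78.2% |
| 30 / 18 | relative risk 0.6 | 78.8% | 68.5% | 61.3% |
| 40 / 22.2 | odds ratio 0.4286 | 91.3% | 91.8% | 86.3% |
| 30 / 15.5 | odds ratio 0.4286 | 87.4% | 85.3% | 78.7% |
| 40 / 20 | difference 20 points | 95.0% | 96.9% | 93.1% |
| 30 / 10 | difference 20 points | 97.8% | 99.3% | 97.3% |

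With all 57 evaluable, the relative-risk and odds-ratio ceilings are about one point higher. The ceiling applies only if the 0.25 guide is always followed. SAP 1.5.1 makes it non-binding, and Protocol 4.1 has the p-value read on a continuous scale.

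**Type I error.** Two comparisons at one-sided 0.027 with a shared control (correlation 0.5) give a family-wise rate of 4.9%. Simulation at control rates of 50%, 40% and 30%, with no stopping, gives 4.7% to 4.8%. A lower event rate costs power, not validity.

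**What a remedy would buy.** A blinded rule was simulated that enlarges the trial when fewer than 33% of 162 pooled patients have the event, capped at 264 randomised per arm.
- At a 40% control rate with one effective arm it triggers 33% of the time and lifts overall power from 76.7% to 81.0%.
- At 30% it lifts overall power from about 60% to 80.6% (one effective arm) or 82.8% (both).
- At 50% with both arms effective, where the design is already right, it still triggers 16% of the time.
- The implied control rate is imprecise. The pooled standard error is √(0.33 × 0.67/162) = 0.037. Dividing by 0.733, the ratio of pooled to control rate if both arms work ((0.5 + 0.3 + 0.3)/3 ÷ 0.5), gives about 5 points.
- At the cap the trial would be 3 × 264 = 792, against 456.

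**The case for a change.** The strongest case for a change is that the plan foresees effective background treatment yet never checks its effect on the event rate. The loss could be large: 61% rather than 90% in the worst case examined. Even if every arm continued past stage 1, final power alone would be 85% or 68% at control rates of 40% or 30% with the relative risk held. Holding the 20-point gap needs a relative risk of 0.50 or 0.33, stronger than the design's 0.6. A review with no timetable could also come after stage 1, too late to help.

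The arithmetic stands, and so does the observation that no quantitative rule exists and that the 50% is undated. The inference that the plan contradicts itself does not stand.
- The clause on all participants receiving one treatment is a contingency. The same SAP section also provides for too few antiviral recipients to adjust for.
- The low-event-rate clauses concern model stability; adjusting for a prognostic covariate does not forecast the control rate.
- Eligibility selects hospitalised grade 3 or 4 patients with radiological change and CRP of at least 30 mg/L, so their rate need not fall in step with general improvements in care.
- The roughly 30% deterioration in Protocol 1.3 is a narrower outcome in a broader population and does not contradict the 50%.
- The promised review has a trigger (a superior therapy emerging) and a forum (the DMC). Protocol 10.3 lets the DMC call for analyses as often as emerging data from this and other studies warrant, and advise on continued recruitment.

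**Conclusion.** No change is called for. The stated 92% and 90% are delivered under the stated 50% to 30%, and neither document reports a lower control rate. The possible shortfall is real but hypothetical: overall power of 78% or 61% (relative risk held), 86% or 79% (odds ratio held), or a gain to 93% or 97% (difference held) at control rates of 40% or 30%. These figures assume 54 and 144 evaluable per arm, unadjusted tests and a stopping guide that is always followed.

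The date and source of the 50% are missing detail that the trial team and DMC can supply when they discuss a change of care. Re-quoting power at another control rate would alter no estimate, interval or decision; the final report will give odds ratios with 95% intervals and a risk difference, which show the precision achieved. Enlarging the trial is a defensible option but a trade-off: it needs a protocol amendment and up to 264 rather than 152 per arm, its trigger and scale are debatable, and its gain at a 40% control rate with one effective arm is about 4 points. Leaving this to DMC judgement, with type I error protected at any event rate, is a fair choice.
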